## PROMIS Integration Phase II (HUM00149448)

**Table 3. Study Measures/outcome Variables**

Measure/variable name	Description	Type
PROMIS Numeric Rating Scale v1.0 – Pain Intensity 1a	Patient reported rating of average pain intensity over the last 7 days (instrument, 1 item)	Continuous. Ranges from 0 (no pain) to 10 (worst pain you can think of)
PROMIS Physical Function Computer Adaptive Test (CAT)	Patient reported ability to do activities of daily living (computer adaptive test instrument)	Continuous. T-score ranges from approximately 20 (extreme impairment)-80 (no impairment)
PROMIS Sleep Disturbance CAT	Patient reported sleep quality (computer adaptive test instrument)	Continuous. T-score ranges from approximately 20 (no problems with sleep)-80 (severe problems with sleep)
Interpersonal Processes of Care Survey	Patient reported quality of patient-provider communication (instrument, 29 items) [24]	Continuous scores for 7 domains: hurried communication, elicited concerns/responded, explained results/medications, patient-centered decision making, compassion, discrimination, and disrespectful office staff. Scores range from 1-5 for each domain.
Discussion of PRO scores with patient during the appointment	Patient report of whether the physician discussed the PRO scores during the appointment (post-appointment survey question).	Binary
Satisfaction with rheumatology care	Leeds Satisfaction with Care Questionnaire (post-appointment survey) [26]	Continuous. Score ranges from 1-5, with higher value indicating greater satisfaction.
Satisfaction with treatment	Treatment Satisfaction Questionnaire for Medication 1.4 (post-appointment survey) [25]	Continuous. Measures 4 domains, including Effectiveness, Side Effects, Convenience, and one global scale item, Global Satisfaction; each domain score ranges from 0-100, with higher score indicating greater satisfaction.
Documentation of PRO scores in the EMR note	Whether the HCP imported the PRO scores into the EMR note (outcome)	Binary

## PROMIS Integration Phase II (HUM00149448)

Interpretation of PRO scores	Whether the HCP interpreted the PRO scores (outcome)	Binary
Clinical decision	What decision was taken at the appointment to address the patient's issues (outcome).	Categorical. Possible decisions include: medication change, referral to another provider, and no action taken.

### 3.6.2.5. Qualitative Assessment of the PRO Integration Process

We will use a combination of qualitative interviews with patients and HCPs participating in the study, and open-ended survey questions to identify the barriers and facilitators to integrating PROs into the clinical workflow, as well as the reasons these barriers and facilitators are arising, and how they may be addressed in the future. Using varied sources of information collected from different stakeholders (patients and HCPs) and at different times will allow us to develop a more objective and richer picture of how the PROs fit into the clinical workflow and how to facilitate increased uptake and more effective usage in the future.

The RE-AIM model will [31] be used to guide investigation of specific aspects of implementation, including recruitment and retention of patient and HCP participants, the impact of interventions on study outcomes, adaptations made to the interventions during the study, factors influencing use of PROs during the study, intention to continue using PROs after the study, and long-term sustainability of the interventions and behaviors.

#### 3.6.2.5.1. Qualitative Interviews with Patients and HCPs

We will conduct semi-structured interviews with up to 10 patients from Arm 1 to understand patients' perspectives on how the PRO information was discussed and used during their appointments, and how PROs fit into their overall care. Interviews will take place after completion of the three (3) month PROMIS questionnaire. During interviews, patients will be asked to discuss their rheumatic disease status, their needs and expectations for the appointment, how the PRO information was discussed or used during the appointment, what decisions were made to address their needs, and their satisfaction with the appointment.

We will also conduct semi-structured interviews with up to 5 HCPs who have patients in Arm 1. During the interview, HCPs will be asked to discuss their experience using PROs in clinical practice, what went well/not well, why, and what changes could help facilitate integration of PROs into practice. HCP interviews will take place toward the end of the study.

Interviews for both patients and HCPs will be conducted via telephone or Zoom Health, and will be recorded and transcribed. Transcripts will be deidentified before analysis to protect interviewees' privacy.

## PROMIS Integration Phase II (HUM00149448)

### 3.6.2.5.2. Open-ended Survey Questions

Open-ended survey questions will be included in the post-appointment survey for patients and the 3-month follow-up surveys for patients.

These questions will allow patients to communicate anything they think is relevant about their experience which cannot be otherwise conveyed through the remaining survey questions.

### 3.7. Study Analyses

Our data sources for this study will be electronic medical records (EMR), survey responses collected through REDCap, and qualitative data collected through semi-structured interviews. We will utilize the Data Direct tool to assist with exporting quantitative data from the EMR, and the EMERSE tool to assist with reviewing textual data from the EMR (<https://research.medicine.umich.edu/our-units/data-office-clinical-translational-research/data-access/self-serve-data-tools>).

#### 3.7.1. Statistical Analysis

##### Sample Size Calculation:

Up to 300 patients will be randomized. Based on our preliminary review, we believe that 70% of the consented patients will meet the inclusion criteria with concerning zone. We expect to screen up to 1,000 patients to meet the randomization goals.

The current study is a convenience sample size since we don't have a priori data to calculate sample size. We believe that approximately 300 patients randomized in 1:1 fashion will give robust point estimates to design a Phase 3 trial.

##### Planned Analyses:

Characteristics of patients will be summarized descriptively, by treatment group and overall, using numerical and graphical methods. We will compare Intervention groups on baseline characteristics, including demographics and PRO measurements, using descriptive statistics. Fisher's exact test and ANOVA/Kruskal-Wallis will be used to comparing the three treatment arms.

For categorical outcomes, count and proportion and 95% confidence interval will be reported. For continuous outcomes, mean, standard deviation, median, and inter-quartile range will be reported. P value < 0.05 will be considered statistically significant.

T-scores for the physical function, sleep disturbance and actual score on 0-10 scale for pain intensity at baseline and 3 month follow-up will be calculated based on the guidelines provided by [http://www.healthmeasures.net/media/kunena/attachments/257/PROMIS29\\_Scoring\\_08082018.pdf](http://www.healthmeasures.net/media/kunena/attachments/257/PROMIS29_Scoring_08082018.pdf).

The planned statistical analyses will enable us to assess the feasibility of the study and assess the potential effects of the interventions. The information gained from this project will help us design the

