## PROMIS Integration Phase II (HUM00149448)

### Patient-Reported Outcomes Measurement Information System (PROMIS) Integration into Rheumatology Clinical Practice

#### Pilot Trial

##### 1.0. Background

Chronic medical conditions, such as rheumatic diseases (RD), have a detrimental effect on self-reported physical, mental, and social health, i.e., health-related quality of life (HRQOL) [1, 2]. RDs are diverse with variable impact on HRQOL, can fluctuate over time, and may mirror disease flares [3-5]. A patient-reported outcome (PRO) is any report of the status of a patient's health condition that comes directly from the patient, without interpretation of the patient's response by a clinician or anyone else [6]. PROs can supplement clinical decision making by aiding assessment and management of these conditions. There is increased enthusiasm within the rheumatology research community to integrate PRO measures with clinical assessments [7-9].

The National Institutes of Health Patient-Reported Outcomes Measurement Information System (PROMIS®) Roadmap initiative (available at <http://www.nihpromis.org>) is a cooperative research program designed to develop, evaluate, and standardize item banks to measure PROs across patients with varying medical conditions and in a cross section of the US population [10]. PROMIS® aims to use item response theory (IRT) to develop reliable and valid item banks that can be administered as short forms and computerized adaptive tests (CAT) [11, 12]. As it improves measurement precision, it lessens burden on the patient. PROMIS short forms are available for incorporation in the electronic medical records [13].

The overarching aim of our project is to lay the groundwork for a well powered randomized controlled trial to assess the impact of incorporating PROs – specifically PROMIS questionnaires – at the point of care in clinical rheumatology practice. This IRB application is for a pilot study to assess the feasibility of a future randomized controlled trial (RCT) of strategies to promote review and discussion of PROs during rheumatology consultations. The current pilot trial will yield important preliminary results to help us design a future RCT, including assessment of the following:

- Recruitment and retention
- Data collection procedures
- Required resources and management capacity
- Intervention acceptability and feasibility
- Expected intervention effect and variability

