## PROMIS Integration Phase II (HUM00149448)

**Table 2. Primary, Secondary, and Exploratory Endpoints**

Assessment	Description	Timeframe
PRIMARY ENDPOINTS		
Percent of appointments at which PROMIS scores are documented in the EMR note by the participating HCP	Documentation in EMR notes will be categorized as either 'yes' or 'no' and identified through EMR data pulls.	Each appointment with the HCP during the trial period
SECONDARY ENDPOINTS		
Percent of appointments at which referrals/recommendations related to PROMIS scores are documented in the EMR note by the participating HCP	Documentation in EMR notes will be either 'yes' or 'no' and identified through EMR data pulls.	Each appointment with the HCP during the trial period
Quality of patient-provider communication	Patient-reported assessment of different aspects of patient-provider communication using the Interpersonal Processes of Care (IPC) Survey (29 items), which measures 7 subscales: hurried communication, elicited concerns/responded, explained results/medications, patient-centered decision making, compassion, discrimination, and disrespectful office staff (score for each subscale ranges from 1-5; a higher score indicates better IPC) [24].	Up to 2 weeks after baseline appointment
Change in score of the most bothersome PROMIS domain from baseline to 3 months	Change in the T-score of the most bothersome PROMIS domain at baseline for sleep disturbance and physical function domains, and change in actual score on a scale 0-10 for pain intensity domain.	3 months post-baseline appointment
EXPLORATORY ENDPOINTS		
Percent of participants reporting discussion of PROs with their rheumatology provider during appointments	Patient report of whether or not PROs were discussed during appointment (assessed via survey).	Up to 2 weeks after baseline appointment

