### 3.6.2. Controlled Trial

#### 3.6.2.1. Trial Study Design

There will be two arms (1: 1 randomization) of the trial to assess PRO integration into care (Figure 3).

- Arm 1: PRO Integration into Clinical Practice Intervention Group
- Arm 2: Usual Care Control Group

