## PROMIS Integration Phase II (HUM00149448)

- Patient will be asked to complete a single-item survey to rank the PRO domains in order of importance.
- Depending on what domain patients indicate is the most concerning to them, patients will be placed into one of 3 groups: "Concerning pain", "Concerning sleep", or "Concerning physical function".

A permuted block randomization scheme stratified by most concerning PRO domain (pain, sleep, physical function) will be created before enrollment begins. Once a participant has completed the screening and evaluation for inclusion/exclusion criteria, the participant will enter the randomization process. Participants will be randomized to Arm 1 and Arm 2 with equal probability (1:1) in RedCap. At time of randomization, the investigator or study coordinator will use the randomization sheet to obtain the assigned randomization number and intervention assignment. In this study, participants and physicians will know the assigned treatment group.

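### The analysis text names three arms in a two-arm trial, and nowhere specifies a between-arm difference with a 95% CI or adjustment for stratum or baseline score

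*Combined protocol and SAP*

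**What the plan says.** Section 3.6.2.1 fixes the design: "There will be two arms (1: 1 randomization) of the trial to assess PRO integration into care". Section 3.6.2.3 adds the stratification: "A permuted block randomization scheme stratified by most concerning PRO domain (pain, sleep, physical function) will be created before enrollment begins".

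Planned Analyses in 3.7.1 then says of the tests: "exact test and ANOVA/Kruskal-Wallis will be used to comparing the three treatment arms". This sentence comes straight after the one on comparing baseline characteristics. On reporting, it says "For categorical outcomes, count and proportion and 95% confidence interval will be reported". Continuous outcomes get mean, SD, median and inter-quartile range only.

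The pilot's purpose is partly estimation. Section 1.0 lists among its products "Expected intervention effect and variability", and the sample size text says that about 300 patients "will give robust point estimates to design a Phase 3 trial".

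In Table 2 the primary endpoint is a percentage of appointments, timed at each HCP appointment in the trial period; 3.6.2.4 likewise assesses process measures at each appointment. A secondary endpoint is "Change in score of the most bothersome PROMIS domain from baseline to 3 months". It is defined as T-score change for sleep and physical function "and change in actual score on a scale 0-10 for pain intensity domain". Three exploratory endpoints compare change between arms within each domain group. The sleep endpoint's title names physical function as the qualifying domain, while its description names sleep disturbance.

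**The concern.** The arm count is a plain contradiction. The three domain groups are randomisation strata, not arms. If the test sentence covers baseline characteristics only, as its position allows, then no test is named for any outcome.

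The larger gap is the missing estimand. A team designing the next trial needs the size of the effect and its uncertainty. A confidence interval for each arm's proportion does not give that directly, and continuous outcomes get no interval at all. The stratum and baseline scores are collected but no analysis uses them as covariates.

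Two rules are also left open. Nothing says what happens when a patient has more than one appointment. Nothing says how a 0-10 pain change, a sleep T-score change and a physical function T-score change are combined, although physical function runs in the opposite direction (2.0, Phase 2).

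**Working it through.** There is no plan figure to reproduce: 3.7.1 calls 300 a convenience sample and gives no effect size, SD, control rate or power. The figures below use 150 per arm and no dropout. They are for scale.

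1. **Do the named tests survive with two groups?** Yes. In a simulated two-group check, ANOVA and the t-test gave the same p-value (0.1422), and so did Kruskal-Wallis and Wilcoxon (0.2320). They return p-values, not a difference with a CI.

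2. **What would a difference look like on the primary endpoint?** With one appointment per patient, the half-width is 1.96 × √[(p₁(1−p₁) + p₂(1−p₂))/150]. At 69.2% in both arms (the Phase I Part B import rate, from trained HCPs, used only as an illustration), 1.96 × √(0.4263/150) = 10.4 points. At 50% in both arms it is 11.3, and at 10% in both it is 6.8. The per-arm half-width at 69.2% is 7.4 points, so the per-arm intervals that the plan asks for are not a substitute.

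3. **What does baseline adjustment gain?** In Table 1 (patient cut scores), 24% fall below 35 and 24 + 48 = 72% below 45. A normal fit gives SD = 10/(0.583 + 0.706) = 7.8 and mean 40.5, with 47.5% at or below the entry cut of 40. Selecting that lower part leaves a baseline variance fraction v = 0.35. Then Var(ANCOVA)/Var(change) = (1+ρ)/[(1−ρ)v + 1 + ρ]:
   - ρ = 0.5: 1.5/1.675 = 0.896, CI 5.4% narrower.
   - ρ = 0.6: 1.6/1.74 = 0.920, CI 4.1% narrower.
   - ρ = 0.7: 1.7/1.805 = 0.942, CI about 3% narrower.

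   With 50 physical function patients per arm and ρ = 0.5 (both assumed), the half-width is 2.6 T-score points by ANCOVA and 2.8 by change score.

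4. **What do repeat appointments do?** If a fraction f of patients has two appointments and the rest one, the design effect is 1 + ICC × 2f/(1+f). The ICC (0.3-0.5) and f are assumed. The z-test column is the normal approximation; the Fisher column comes from beta-binomial simulations at 69.2%.

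| Share with two appointments | Design effect | Type I error, z test | Type I error, Fisher |
|---|---|---|---|
| None | 1.00 | 5.0% | about 4% |
| A quarter | 1.12-1.20 | 6.4-7.4% | about 5-6% |
| All | 1.30-1.50 | 8.6-11.0% | about 7-10% |

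   If all patients have two, the correct CI is √1.30 to √1.50, or 1.14 to 1.22, times the naive one.

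5. **What would raw pooling do?** Assume a 0.3 SD benefit in every domain, with SDs of 2 (pain), 8 (sleep) and 7.8 (physical function). The raw changes are −0.6, −2.4 and +2.34. The pooled mean is:
   - equal shares: (−0.6 − 2.4 + 2.34)/3 = −0.22;
   - pain 40%, sleep 40%, physical function 20%: −0.24 − 0.96 + 0.468 = −0.73;
   - pain 20%, sleep 20%, physical function 60%: −0.12 − 0.48 + 1.404 = +0.80.

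   The sign follows the mix of strata, although every patient benefits equally. In simulations varying shares and SDs (correlation 0.5), raw pooling had power 0.02-0.28, against 0.82-0.87 for an aligned, standardised ANCOVA.

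**The case against.** The strongest reply is that this is a convenience-sample pilot that leaves the formal test to the next trial, that three for two is a slip, and that a crude difference can be computed from the per-arm summaries. All of that is fair, and it keeps the core point modest. It does not remove it: pilot status excuses a missing power calculation, but not a missing effect estimate when that estimate is a stated product.

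A reader might infer four stronger things, which the documents do not support.

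- **That no between-arm comparison is planned.** Table 2 compares change between arms within each domain group, and those comparisons use baseline by subtraction. The conflict in the sleep endpoint's title does need correcting.
- **That the primary test is known to be inflated.** Fisher's test may be meant for baseline only. The 12-month period in 3.3 may be a recruitment window, since it can also end when the sample is reached. Figure 4 shows one emailed report, at baseline. Two appointments for every patient has no source, so the 7-10% is an upper scenario.
- **That raw pooling is planned.** No section says so, and the plan states each scale and its direction. The power loss describes an analysis that nobody has proposed.
- **That the missing adjustment makes the analysis invalid.** It costs some precision.

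**Conclusion.** The point holds as a specification gap that should be closed before analysis. Three parts rest on the text alone: the wrong arm count, the absence of a between-arm difference with a 95% CI, and the absence of adjustment for stratum or baseline score. Their cost is clarity plus about 3-5% in interval width, given an assumed baseline to 3-month correlation of 0.7-0.5 and the Table 1 fit.

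The two open rules matter more, but only conditionally. The primary endpoint's error rate rises above the one-appointment level only if repeats occur and are treated as independent, and the amount depends on how many patients have them. The most bothersome domain result is misleading only if raw changes are pooled. Neither harm arises with one appointment per patient and no raw pooling. The plan should say so in advance.

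**What to change.** - **Arm count:** change three to two in Planned Analyses, and state whether the sentence covers baseline, outcomes or both.
- **Binary endpoints:** Mantel-Haenszel risk difference with 95% CI, stratified by most concerning domain. For the appointment-based endpoints, the primary analysis uses the baseline appointment, one per patient. This also avoids appointment counts that arise after randomisation and could differ by arm. Analyse all appointments only as a sensitivity analysis with patient-clustered standard errors. Do not use unadjusted appointment-level tests.
- **Domain-specific 3-month endpoints:** first correct the sleep endpoint's title to match its description. Then use ANCOVA of the 3-month score on arm and baseline score within each domain, with the adjusted difference and 95% CI.
- **Most bothersome domain endpoint:** align direction, divide each domain by its baseline SD over all randomised patients (3.4 requires all three measures), and adjust for standardised baseline and stratum. Present the domain-specific differences in score points alongside.
- **IPC, TSQM and Leeds:** mean difference with 95% CI, adjusted for stratum.

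The cost is wording and code. Stratum, baseline scores and appointment records are already collected. The downsides are a modelling assumption, less familiar SD units for the pooled endpoint, and later appointments moved to a sensitivity analysis.

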## **PROMIS Integration Phase II (HUM00149448)**

next trial to formally test the effect of PRO integration on communication, decision making, and health outcomes.

### **3.7.2. Analysis of Qualitative Data**

The qualitative data gathered will include transcriptions of interviews and free text comments from post-appointment surveys. Analysts will code the deidentified data using CAQDAS software such as NVIVO. The analysts will perform inter-rater reliability checks periodically to ensure coding is reconciled. Coded concepts will be organized into themes describing barriers and facilitators to PRO integration into clinical practice, and ways to facilitate more effective PRO integration and uptake in the future.

